11 STUDY MANAGEMENT AND ADMINISTRATION

11.1 Adherence to protocol

The investigator should not deviate from the protocol. However, the investigator should take any measure necessary in deviation from or not defined by the protocol in order to protect clinical study subjects from any immediate hazard to their health and safety. In this case, this action should be taken immediately, without prior notification of the regulatory authority, IRB/IEC, or sponsor.

After implementation of such measure, the investigator must notify the Clinical Project Manager of the sponsor within 24 hours and follow any local regulatory requirements.

11.2 Monitoring

UCB (or designee) will monitor the study to meet the sponsor's monitoring Standard Operating Procedures (SOPs), ICH-GCP guideline, and applicable regulatory requirements, and to ensure that study initiation, conduct, and closure are adequate. Monitoring of the study may be delegated by UCB to a contract research organization (CRO) or a contract monitor.

The investigator and his/her staff are expected to cooperate with UCB (or designee) and to be available during the monitoring visits to answer questions sufficiently and to provide any missing information. The investigator(s)/institution(s) will permit direct access to source data/documents for study-related monitoring, audits, IRB/IEC review, and regulatory inspection(s).

The investigator will allow UCB (or designee) to periodically review all CRFs and corresponding source documents (eg, hospital and laboratory records for each subject). Monitoring visits will provide UCB (or designee) with the opportunity to evaluate the progress of the study, verify the accuracy and completeness of CRFs, ensure that all protocol requirements, applicable authorities regulations, and investigator's obligations are being fulfilled, and resolve any inconsistencies in the study records.

11.2.1 Definition of source data

All source documents must be accurate, clear, unambiguous, permanent, and capable of being audited. They should be made using some permanent form of recording (ink, typing, printing, optical disc). They should not be obscured by correction fluid or have temporary attachments (such as removable self-stick notes). Photocopies of CRFs are not considered acceptable source documents.

Source documents are original records in which raw data are first recorded. These may include hospital/clinic/general practitioner records, charts, diaries, x-rays, laboratory results, printouts, pharmacy records, care records, ECG or other printouts, completed scales, or quality of life questionnaires, for example. Source documents should be kept in a secure, limited access area.

Source documents that are computer generated and stored electronically must be printed for review by the monitor (eg, ECG reports). Once printed, these copies should be signed and dated

by the investigator and become a permanent part of the subject's source documents. The investigator will facilitate the process for enabling the monitor to compare the content of the printout and the data stored in the computer to ensure all data are consistent.

Electronic data records, such as Holter monitor records or electroencephalogram records, must be saved and stored as instructed by UCB (or designee).

11.2.2 Source data verification

Source data verification ensures accuracy and credibility of the data obtained. During monitoring visits, reported data are reviewed with regard to being accurate, complete, and verifiable from source documents (eg, subject files, recordings from automated instruments, tracings [ECG], x-ray films, laboratory notes). All data reported on the eCRF should be supported by source documents, unless otherwise specified in Section 11.2.1.

11.3 Data handling

11.3.1 Case Report form completion

The study will be performed using remote data capture (RDC). The investigator is responsible for prompt reporting of accurate, complete, and legible data in the electronic CRFs and in all required reports.

Any change or correction to the electronic eCRF after saving must be accompanied by a reason for the change.

Corrections made after the investigator's review and approval (by means of a password/electronic signature) will be reapproved by the investigator.

The investigator should maintain a list of personnel authorized to enter data into the electronic eCRF.

Detailed instructions will be provided in the eCRF Completion Guidelines.

11.3.2 Database entry and reconciliation

Case Report forms/external electronic data will be entered/loaded into a validated electronic database using a clinical data management system (CDMS). Computerized data cleaning checks will be used in addition to manual review to check for discrepancies and to ensure consistency of the data. This study is performed using RDC; the data are entered into the electronic CRFs once and are subsequently verified.

An electronic audit trail system will be maintained within the CDMS to track all data changes in the database once the data have been saved initially into the system or electronically loaded. Regular backups of the electronic data will be performed.

11.3.3 Subject Screening and Enrollment log/Subject Identification Code list

The subject's screening and enrollment will be recorded in the Subject Screening and Enrollment Log.

The investigator will keep a Subject Identification Code list. This list remains with the investigator and is used for unambiguous identification of each subject.

The subject's consent and enrollment in the study must be recorded in the subject's medical record. These data should identify the study and document the dates of the subject's participation.

11.4 Termination of the study

UCB reserves the right to temporarily suspend or prematurely discontinue this study either at a single site, multiple sites, or at all sites at any time for reasons including, but not limited to, safety or ethical issues, inaccurate or incomplete data recording, noncompliance, or unsatisfactory enrollment with respect to quality or quantity.

If the study is prematurely terminated or suspended, UCB (or its representative) will inform the investigators/institutions and the regulatory authority(ies) of the termination or suspension and the reason(s) for the termination or suspension, in accordance with applicable regulatory requirement(s). The IRB/IEC should also be informed and provided with reason(s) for the termination or suspension by the sponsor or by the investigator/institution, as specified by the applicable regulatory requirement(s). In addition, arrangements will be made for the return of all unused study drug and other material in accordance with UCB procedures for the study.

11.5 Archiving and data retention

The investigator will maintain adequate records for the study, including medical records, laboratory results, Informed Consent documents, drug dispensing and disposition records, safety reports, information regarding participants who discontinued, and other pertinent data.

All essential documents are to be retained by the investigator until at least 2 years after the last approval of a marketing application in an ICH region and until there are no pending or contemplated marketing applications in an ICH region, or at least 2 years have elapsed since the formal discontinuation of clinical development of the investigational product. These documents should be retained for a longer period, however, if required by the applicable regulatory requirement(s) or by an agreement with UCB (CPMP/ICH/135/95, 2002 [Section 4.9.5]). The investigator will contact UCB for authorization prior to the destruction of any study records or in the event of accidental loss or destruction of any study records. The investigator will also notify UCB should he/she relocate or move the study-related files to a location other than that specified in the sponsor's study master file.

11.6 Audit and inspection

The investigator will permit study-related audits mandated by UCB, after reasonable notice, and inspections by domestic or foreign regulatory authorities.

The main purposes of an audit or inspection are to confirm that the rights and well-being of the subjects enrolled have been protected, that enrolled subjects (ie, signing consent and undergoing study procedures) are appropriate for the study, and that all data relevant for the evaluation of the IMP have been processed and reported in compliance with the planned arrangements, the protocol, investigational site, and IRB/IEC SOPs, ICH GCP, and applicable regulatory requirements.

The investigator will provide direct access to all study documents, source records, and source data. If an inspection by a regulatory authority is announced, the investigator will immediately inform UCB (or designee).

11.7 Good Clinical Practice

Noncompliance with the protocol, ICH-GCP, or local regulatory requirements by the investigator, institution, institution staff, or designees of the sponsor will lead to prompt action by UCB to secure compliance. Continued noncompliance may result in the termination of the site's involvement in the study.

12 STATISTICS

A description of statistical methods follows and will be described in more detail in the Statistical Analysis Plan (SAP).

12.1 Definition of analysis sets

Analysis sets will be defined as follows:

- The Safety Set (SS) will consist of all enrolled subjects who took at least 1 dose of LCM in this long-term study. All safety analyses will be performed on the SS.
- The Full Analysis Set will be used for the analysis of seizure data and will consist of all subjects in the SS, who have at least 1 completed post-Baseline seizure diary.

12.2 General statistical considerations

Descriptive statistics will be used to provide an overview of the safety and efficacy results. For categorical parameters, the number and percentage of subjects in each category will be presented. The denominator for percentages will be based on the number of subjects appropriate for the purpose of analysis. For continuous parameters, descriptive statistics will include n, mean, standard deviation (SD), median, minimum, and maximum. No statistical hypothesis testing will be performed. Baseline values for safety and efficacy variables will be determined from Baseline values of the primary study.

Further methods pertaining to the summary and analysis of the efficacy and safety data are presented in the following sections, and will be described in more detail in the SAP.

12.3 Planned safety analyses

The long-term safety of LCM at individualized doses will be evaluated by means of the safety analyses. Summary tables will be presented over the Treatment Period by 3-month periods and by categories of total duration of exposure. All safety variables will be analyzed by descriptive methods on the SS. Treatment-emergent AEs will be defined as those events which started on or after the date of first EP0034 dose of LCM, or whose severity worsened on or after the date of first EP0034 dose of LCM. Adverse events which occur within 30 days after last dose of LCM will be considered treatment emergent. Treatment-emergent AEs will be summarized by categories of total duration of exposure, 3-month period, Medical Dictionary for Regulatory Activities (MedDRA[®]) Primary System Organ Class and Preferred Term in incidence tables. Separate tables will be provided by categories of total duration of exposure for AEs leading to withdrawal from the study and SAEs.

The safety variables such as changes in ECG, vital signs, laboratory parameters, height, body weight measurements, and Tanner Stage scores will be analyzed descriptively. The results for occurrence of these variables during long-term treatment will be summarized overall, and by visit. Subjects will be grouped by dose for summary purposes. The procedure for grouping

subjects by dose will be defined in the SAP. In addition, shift tables may be used to evaluate the number and percentage of subjects having a different post-Baseline status when compared to their Baseline status.

Changes from Baseline in laboratory, ECG, and vital sign values will be tabulated. In addition, physical and neurological examination abnormalities will be listed by visit. Markedly abnormal values will be summarized descriptively for laboratory, vital sign, body weight, and ECG parameters.

Achenbach CBCL scores, BRIEF/BRIEF-P scores, and Bayley-III scores and the respective change from primary LCM study Baseline scores will be analyzed in a descriptive manner.

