4.1.2 Other safety variables

The other safety variables include the following:

- Safety laboratory tests (hematology; biochemistry including hepatic monitoring of alanine aminotransferase [ALT], aspartate aminotransferase [AST], alkaline phosphatase [ALP], total bilirubin, and gamma-glutamyltransferase [GGT]; endocrinology for all subjects; and urinalysis for subjects ≥ 5 years of age)
- Electrocardiograms
- Physical (Tanner Stage, if applicable depending on subject's developmental status) and neurological examinations
- Vital signs (blood pressure and pulse rate)
- Body weight and height
- Change from Baseline in the Achenbach CBCL score: the Achenbach CBCL/1½-5 for children from 1.5 to 5 years of age and the Achenbach CBCL/6-18 for children ≥ 6 years of age
- Change from Baseline in the BRIEF-P score for subjects ≥ 2 and < 5 years of age
- Change from Baseline in the BRIEF score for subjects ≥ 5 years of age
- Change from Baseline in the Bayley-III scales in subjects < 18 months of age at study entry (applicable only to subjects enrolled in English-speaking countries)

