10.6 Laboratory measurements

Blood and urine specimens for routine assay of hematology, clinical chemistry, endocrinology, and urinalysis testing will be collected according to the tabular schedules of study procedures (Section 5.2). Urine assessments will be performed for subjects aged ≥ 5 years. For subjects aged ≥ 5 years, urine assessments will be based on the subject's ability to void and staff's ability to collect urine (in an appropriate container). A central laboratory will perform the routine analysis of blood and urine specimens. Pregnancy testing will also be performed (see Section 10.7). The procedures for handling and shipping these specimens will be provided to the sites. In exceptional circumstances, local laboratory analysis may be performed. The medical monitor should be contacted beforehand to discuss these circumstances.

The following laboratory parameters will be measured:

Table 10–2: Laboratory measurements

Hematology	Chemistry	Endocrinology	Urinalysis ^a
Hematocrit	Calcium	FSH	pH
Hemoglobin	Phosphorus	LH	Ketones
Platelet count	Serum electrolytes (sodium, potassium, chloride, bicarbonate)	Testosterone	Glucose
RBC count	Creatinine	TSH	Albumin
WBC count	BUN	T ₃ (total and serum free)	Specific gravity
Differential count	AST	T ₄ (total and serum free)	Microscopic exam for blood cells or casts/hpf
	ALT		
	Total bilirubin		
	Alkaline phosphatase		
	GGT		
	Glucose		
	Albumin		
	Total serum protein		
	Uric acid		
	Total cholesterol		
	Triglycerides		

ALT=alanine aminotransferase; AST=aspartate aminotransferase; BUN=blood urea nitrogen; FSH=follicle stimulating hormone; GGT=gamma-glutamyltransferase; hpf=high power field; LH=luteinizing hormone; RBC=red blood cells; T₃=triiodothyronine; T₄=thyroxine; TSH=thyroid stimulating hormone; WBC=white blood cell

^a Urinalysis will be performed for subjects ≥5 years of age only.

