#### **3.9.2 Planned safety analyses**

For planned safety analyses, the protocol states that:

Summary tables will be presented over the Treatment Period by 3-month periods and by categories of total duration of exposure.

However, only select AE tables will be presented by 3-month time intervals; incidence of all TEAEs with onset during the Treatment Period, incidence of all serious TEAEs with onset during the Treatment Period, incidence of drug-related TEAEs, incidence of TEAEs by maximum intensity, incidence of all TEAEs leading to discontinuation with onset during the Treatment Period, and incidence of all other significant TEAEs with onset during the Treatment Period.

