### 8.3 Clinical laboratory evaluations

Hematology, blood chemistry (including liver function tests), urinalysis, and endocrinology parameters are assessed throughout the study, according to the tabular schedules of study procedures. Urinalysis will be performed for subjects  $\geq 5$  years of age only.

All summaries of laboratory parameters will only summarize parameters planned based on the protocol. However, both planned and unplanned laboratory parameters will be provided in subject data listings. Summaries will include hematology, chemistry and endocrinology results; urinalysis results will be included in subject data listings only.

Observed values of hematology, chemistry, and non-gender specific endocrinology parameters (ie, thyroid stimulating hormone, triiodothyronine [total and serum-free], and thyroxine [total and serum-free]) will be summarized for each visit and Last Visit. Change from Baseline for hematology, chemistry, and non-gender specific endocrinology parameters will be summarized for all post-Baseline visits, and Last Visit. Gender specific endocrinology parameters (ie, follicle stimulating hormone, luteinizing hormone, and testosterone) will be presented similarly, by gender.

A shift table that cross-tabulates Baseline versus maximum result during the Treatment Period in categories of  $<1 \times$  ULN (upper limit of normal),  $1$  to  $<2 \times$  ULN,  $2$  to  $<3 \times$  ULN,  $\geq 3 \times$  ULN, and missing will be presented for liver function tests (LFT) which include ALT, AST, GGT, Total Bilirubin, and ALP.

Treatment-emergent markedly abnormal (TEMA) values are defined as those TEMA values during the defined Treatment Period at scheduled or unscheduled visits which occur on or after the first EP0034 LCM administration through to the end of the study but were normal at Baseline. The age at the time of assessment will be used for determining TEMA (as defined in Section 3.2.24).

The number and percentage of subjects with a TEMA value, TEMA low value, and TEMA high value will be summarized, at each post-Baseline visit and Last Visit. Percentages will be relative to the number of subjects with a value at each time point. Criteria for determining if a value is TEMA are detailed in Appendix 12.1.

Serum and urine pregnancy testing will be performed on all females of childbearing potential, according to the tabular schedules of study procedures.

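### SAP 8.3 gives urinalysis in listings only, although Protocol 12.3 promises descriptive analysis of all safety variables and tabulated laboratory changes; SAP 3.9 does not declare the departure

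*Protocol*

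**What the plan says.** **Protocol.** Section 4.1.2 defines the safety laboratory tests as hematology, biochemistry, "endocrinology for all subjects; and urinalysis for subjects ≥ 5 years of age". Section 10.6 treats the four as routine panels ("Blood and urine specimens for routine assay of hematology, clinical chemistry, endocrinology, and urinalysis testing will be collected"), and Table 10-2 lists six urinalysis items: pH, ketones, glucose, albumin, specific gravity, and microscopy for cells or casts. Section 12.3 commits to descriptive analysis of every safety variable on the Safety Set. For a group of variables that includes laboratory parameters it says "The results for occurrence of these variables during long-term treatment will be summarized overall, and by visit". It adds "Changes from Baseline in laboratory, ECG, and vital sign values will be tabulated" and "Markedly abnormal values will be summarized descriptively for laboratory, vital sign, body weight, and ECG parameters". Shift tables are mentioned only as something that may be used.

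**SAP.** Section 2.2.2 repeats urinalysis as a safety variable, and Section 8 opens with descriptive methods for all safety variables. Section 8.3 plans observed values and change from Baseline by visit and at Last Visit for hematology, chemistry and endocrinology, but says that "urinalysis results will be included in subject data listings only". Section 3.9 declares two departures from the protocol. Section 3.9.1 covers added subgroups, and 3.9.2 covers the reduced set of 3-month adverse event tables ("However, only select AE tables will be presented by 3-month time intervals").

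**The concern.** The protocol promises tabulation for laboratory data as a class, and the SAP withdraws it for one named panel without saying that it has done so. The study's primary objective is long-term safety and tolerability. Children aged 5 years or older give urine repeatedly over about 2 years, yet no output would say how many developed new glucose, ketones, albumin, or cells or casts in the urine. A reader who compares the report with the protocol would find an analysis missing, with nothing in the SAP's own record of changes to explain why.

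**Working it through.** The plan gives no figure to reproduce: the study is descriptive and has no formal sample size calculation. The check sets the texts side by side and makes two simple counts.

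**Step 1: is urinalysis within 'laboratory' in Protocol 12.3?** Yes. Sections 4.1.2 and 10.6 and Table 10-2 all place it there. Protocol 12.3 also distinguishes tabulating from listing. In the same paragraph it says that physical and neurological examination abnormalities will be listed by visit, and it does not say this of any laboratory panel.

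**Step 2: what does the SAP provide for each panel?**

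| Panel | Observed values and change from Baseline (SAP 8.3) | Marked-abnormality criteria (SAP Appendix 12.1) |
|---|---|---|
| Hematology | Yes | Yes |
| Chemistry | Yes | Yes |
| Endocrinology | Yes (FSH, LH and testosterone by gender) | Thyroxine (T4) only |
| Urinalysis | No, listings only | None |

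Four panels are named, three are summarised, and one is not. No other SAP output fills the gap. The laboratory shift table covers ALT, AST, GGT, total bilirubin and ALP. The liver injury table uses ALT, AST, bilirubin and symptoms.

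**Step 3: is the departure declared?** SAP 3.9 holds two entries, and neither concerns urinalysis. The second entry declares a partial cut in tables, restricting the 3-month presentation to selected adverse event tables. Removing every summary of a named panel is at least as reportable.

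**Step 4: is the SAP consistent with itself?** No. Section 8 applies descriptive methods to all safety variables. A listing contains no descriptive statistic.

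**Step 5: how much data is affected per subject?** Protocol Tables 5-1 and 5-2 schedule urinalysis at Weeks 0, 20, 52, 72 and 96. The Week 0 sample may be the one taken at the parent study's final Transition Visit.

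5 visits × 6 items = 30 scheduled results for a fully followed child aged at least 5 years throughout.

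Early Termination, Taper and Safety Follow-Up samples come on top where they apply. A study-wide total cannot be derived. The documents say only that approximately 500 subjects may be eligible. They give no age split or expected dropout, and collection depends on the child's ability to void.

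**The case against.** The strongest reply is that Protocol 12 and 12.2 leave detail to the SAP, and that SAP 8.3 states its choice openly. The study is descriptive, several urinalysis items are qualitative, and mean change would suit them badly. This explains why the hematology format should not simply be copied. It does not explain having no table, because Protocol 12.2 already provides counts and percentages for categorical data. Removing a panel's summaries is a withdrawal of a protocol analysis and not added detail.

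Other points on that side do stand, and they limit the finding:

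- A reader might infer that the report could say nothing quantitative about urine, or that a signal would surface only through investigators' adverse event reports. The documents do not support this. SAP 3.1 requires listings of all documented and calculated data, which can be read and counted. Protocol 10.1.8 provides for periodic sponsor review of selected data and gives laboratory results as an example of additional measures.
- Several related blood measures (glucose, albumin, total protein, creatinine, BUN, bicarbonate) are tabulated. They do not cover urinary cells or casts.
- A reader might infer that urinalysis alone lacks abnormality criteria. Endocrinology has none except for T4.
- A reader might treat the missing urinalysis shift table as a breach in itself. Protocol 12.3 makes shift tables optional, so it is not.
- The primary safety variables are three treatment-emergent adverse event incidences. Urinalysis is an 'other' safety variable.

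**Conclusion.** The conflict is real and present in the current texts. SAP 8.3 contradicts Protocol 12.3 and SAP Section 8, and SAP 3.9 does not declare it. The consequence is that no table counts new urinary abnormalities. They remain discoverable in listings, through sponsor review, or as adverse events, but none of these is a planned incidence. The impact is modest: it touches no primary safety variable and no hypothesis test. It should still be corrected, because the data are collected, the protocol promised the analysis, and the correction is cheap. The conclusion rests only on reading 'laboratory' in Protocol 12.3 as including the panels that Protocol 4.1.2 and Table 10-2 place under that name. It does not depend on any assumed number of subjects.

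**What to change.** In SAP 8.3, replace the listings-only sentence with two outputs, both restricted to subjects aged 5 years or older at the assessment who have a urine sample:

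1. **pH and specific gravity:** observed values and change from Baseline, by visit and at Last Visit.
2. **Ketones, glucose, albumin and microscopy:** number and percentage by result category, plus a shift from Baseline to the worst on-treatment result and to Last Visit. Define abnormal by the central laboratory's reference flag. This assumes that the laboratory supplies one for each item, which the documents do not state and the sponsor should confirm.

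The shift table needs a 'missing' Baseline category. SAP 3.3 takes Baseline from before the first lacosamide dose in the parent study, so a child who was then under 5 and reaches 5 later may have no Baseline urinalysis. How many such children there are depends on parent-study collection rules that these documents do not give.

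If the sponsor prefers to keep listings only, the minimum is an entry in SAP 3.9 that declares and justifies the departure, with SAP Section 8 reconciled to it. That removes the documentation gap but still leaves no counts.

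The cost is a change of SAP wording and two additional tables, with no new data collection.
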